7.4 Serious Adverse Events (SAE)

SAE is defined as any significantly untoward medical occurrence, including:

- Death
- Life-threatening condition
- Inpatient hospitalization or prolongation of existing hospitalization
- Persistent or significant disability/incapacity
- Congenital anomaly/birth defect
- Required intervention to prevent permanent impairment/damage

7.5 Serious and Unexpected Suspected Adverse Reaction

(SUSAR)

SUSAR is defined as any significantly untoward medical occurrence, the nature or severity of:

1. Which is not consistent with the applicable product information (e.g., Investigator's Brochure) for an unapproved investigational medicinal product.
2. Which must be causal relationship with study medication or clinical study.

7.6 SAE Report Procedure

7.6.1 Expedited Reporting of SAEs

Since the clinical study is to be carried out in U.S. and Taiwan, when expedited SAEs meet the informed criteria according to the relevant regulations, they will be reported to the Food and Drug Administration (FDA), U.S. and Minister of Health and Welfare (MOHW), Taiwan by the Sponsor. Written reports should be made on the ADR Reporting Form on Med watch 3500A Form of US FDA and of Taiwan MOHW, and submitted in a timely fashion according to all relevant regulatory requirements. A copy of this report will also be provided to the principal investigator's local institutional review board if necessary. All SAEs will be monitored until they are resolved or until the principal investigator assesses them as irreversible, chronic, or stable, or until the subject dies. During the clinical trial, if expedited SAEs occur, the investigator should inform the sponsor/CRO within 24 hours by fax and/or telephone.

7.6.2 IRB Notification

Reports of serious adverse events will be communicated to IRB:

- Fatal or life-threatening SUSAR: Should be reported to IRB in the 7 calendar days and detailed written documents should be provided within 15 days after being aware of the event.
- Non-Fatal or life-threatening SUSAR: Should be reported to IRB no later than 15

calendar days.

- Non-SUSAR SAE: Should be reported to IRB following each IRB regulations.

7.6.3 Record Retention

All telephone/fax reports must be followed with a written narrative summary of the adverse event and any sequel. These narratives, which confirm the information collected by telephone and may provide additional information not available at the time of the initial report, must be reviewed by the clinical monitor within 7 calendar days following the telephone/fax report to sponsor.

8. Statistic Methods

8.1 Sample Size Determination

In part II, this is a small proof-of-concept study to evaluate low-dosed PDC-1421 arm, high-dosed PDC-1421 arm and placebo arm in the treatment of ADHD. A two stage design developed by Jung (2008) with $\alpha=0.15$ and power=80% will be used. We estimated that the PDC-1421 is considered non-effective if the response rate based on ADHD Rating Scale – Investigator Rated (ADHD-RS-IV) is 20 % or lower and is worth further study if the response rate is 40 % or higher. At the first stage, we recruit 23 subjects for each group. If the difference between the numbers of responders for any PDC-1421 arm and control arm is greater or equal to 0, we proceed to the second stage. We will recruit 10 subjects for each group at the second stage. If the difference between the accumulated numbers of responders for any PDC-1421 arm and control arm is less than 4, we reject the drug. The minimum sample size required is to recruit 69 subjects, while the maximum sample size is 99. No multiple comparison will be applied.

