3.1 General Design

Table 11. Summary of general design

	Phase II Part II
Design	Double-blind, randomized, parallel group, placebo-controlled
ADHD patients	Stage I: 69 Stage II: 30
Treatment	Randomly assigned on a 1:1:1 basis to one of the three arms: (1) 1 PDC-1421 Capsule plus 1 placebo TID (2) 2 PDC-1421 Capsule TID (3) 2 Placebo TID for 56 days There will be an interim analysis between stage I and stage II.
Assessment interval	Biweekly
Efficacy and safety evaluation	
 • Primary endpoint: efficacy measurement (ADHD-RS-IV) • Secondary endpoints: other efficacy and safety measurements (ADHD-RS-IV, CAARS-S:S, CGI-I, E-SCT, ECG, vital sign, physical examination, hematology, blood chemistry and concomitant medication evaluation)

The Screening phase is intended for diagnosing and assessing the patient for possible inclusion in the study and for providing an adequate washout period. The targeted population of this Part II study is 99 subjects who met the intent-to-treat basis.

[figure not shown]
Part II is a randomized, double-blind, placebo-controlled, parallel-group study.

Stage I: Sixty nine subjects will be randomly assigned on a 1:1:1 basis to one of the three treatment arms (1 PDC-1421 Capsule plus 1 placebo TID, 2 PDC-1421 Capsule TID, 2 placebo TID). Each subject will be treatment for 8 weeks and will return for visit biweekly during the treatment period.

An interim analysis: An interim analysis will be conducted to evaluate the efficacy of PDC-1421 and to decide whether it is necessary enter the second stage of Part II. (See [Section 8](#) for evaluation details.)

Stage II: Thirty subjects will be randomly assigned on a 1:1:1 basis to one of the three treatment arms (1 PDC-1421 Capsule plus 1 placebo TID, 2 PDC-1421 Capsule TID, 2 placebo TID). Each subject will be treatment for 8 weeks and will return for visit biweekly during the treatment period.

Figure 2. General design of procedure

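### The final go/no-go rule, as written, rejects the drug if either dose falls short, and the stated alpha of 0.15 and power of 80% fit only one dose against placebo

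*Protocol*

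**What the plan says.** Protocol 8.1 adopts a published two-stage design with alpha 0.15 and power 80%. The drug counts as non-effective if the response rate "is 20 % or lower and is worth further study if the response rate is 40 % or higher". No separate placebo rate is given.

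- **Allocation** (Protocol 3.1): "Randomly assigned on a 1:1:1 basis to one of the three arms", so both doses are compared with the same placebo group.
- **Stage I** (Protocol 8.1): "At the first stage, we recruit 23 subjects for each group". The trial continues if the difference in responders "for any PDC-1421 arm and control arm is greater or equal to 0, we proceed to the second stage".
- **Stage II** (Protocol 8.1): "We will recruit 10 subjects for each group at the second stage".
- **Final rule** (Protocol 8.1, same sentence in SAP 5.3.4): "If the difference between the accumulated numbers of responders for any PDC-1421 arm and control arm is less than 4, we reject the drug".
- **Multiplicity** (Protocol 8.1): "No multiple comparison will be applied". Protocol 8.2 gives the small proof-of-concept setting as the reason for not adjusting pairwise p-values, and SAP 6.8.2 repeats the policy.

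SAP 5.3.4 lays out the stage I gate separately for high dose minus placebo and low dose minus placebo. Neither document says whether 0.15 and 80% apply to each dose or to the decision on the drug.

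**The concern.** The word *any* works in opposite directions at the two looks. At stage I one dose at or above placebo is enough to continue. At the end, taken at its word, one dose short of 4 is enough to reject the whole drug, whatever the other dose did. That sits badly with Protocol 6.2, which wants the final report to establish which dose group or groups are efficient.

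The alternative reading, that the drug fails only when both doses fall short, gives the opposite verdict whenever exactly one dose reaches 4. The rule decides whether the drug goes forward, so its meaning should not depend on the reader, and the quoted error rates should belong to the decision actually taken.

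**Working it through.** **Inputs.** 23 then 10 subjects per arm, stage I cut 0, final cut 4, response rates 0.20 and 0.40 (all Protocol 8.1); two doses and one shared placebo arm (Protocol 3.1). The placebo rate is an assumption: 0.20 as the base case, with a range below.

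**Step 1: reproduce the stated pair.** Let D1 and D2 be the differences in responders, one dose minus placebo, at stages I and II. Each is a difference of two independent binomial counts (n = 23, then n = 10). Then

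P(go) = P(D1 ≥ 0 and D1 + D2 ≥ 4) = Σ over d ≥ 0 of P(D1 = d) × P(D2 ≥ 4 − d).

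Exact enumeration gives:

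| Final cut | Alpha (0.20 v 0.20) | Power (0.40 v 0.20) |
|---|---|---|
| 3 | 0.216 | 0.864 |
| **4** | **0.139** | **0.801** |
| 5 | 0.082 | 0.719 |

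A cut of 4 is the one that fits 0.15 and 80%. The plan's calculation is therefore sound, and it is a calculation for one dose against placebo.

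**Step 2: the decision on the drug.** Given the placebo counts, the two dose arms are independent. So the two-dose probabilities follow by enumerating each dose conditionally and summing over the placebo counts. Stage II opens if either dose passes stage I.

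| True rates (placebo, dose, dose) | Both doses reach 4 (literal rule) | At least one reaches 4 | Exactly one reaches 4 |
|---|---|---|---|
| 0.20, 0.20, 0.20 | 0.047 | 0.232 | 0.232 − 0.047 = 0.185 |
| 0.20, 0.20, 0.40 | 0.133 | 0.808 | 0.808 − 0.133 = 0.675 |
| 0.20, 0.40, 0.40 | 0.685 | 0.921 | 0.921 − 0.685 = 0.236 |

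Requiring each dose to pass its own stage I gate, as the SAP table suggests, hardly matters: 0.046, 0.132 and 0.681 for both doses; 0.231, 0.808 and 0.921 for at least one. Two million simulated trials per scenario agreed with the enumeration to within 0.001.

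The last column is the probability that the two readings give opposite verdicts: about two trials in three when exactly one dose works.

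For scale, two independent tests at 0.15 would give 1 − 0.85² = 0.2775. The figure here is lower because the attained per-dose alpha is 0.139 and the doses share a placebo arm.

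**Step 3: dependence on the common null rate.**

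| Rate in all arms | Per-dose alpha | At-least-one-dose false-go |
|---|---|---|
| 10% | 0.073 | 0.133 |
| 20% | 0.139 | 0.232 |
| 22% | 0.147 | 0.244 |
| 23% | 0.151 | 0.249 |
| 25% | 0.158 | 0.259 |
| 30% | 0.171 | 0.277 |
| 40% | 0.187 | 0.297 |
| 50% | 0.192 | 0.302 |

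Per-dose alpha passes 0.15 between 22% and 23%.

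**The case against.** The strongest reply is that the figures were meant dose by dose. SAP 5.3.4 sets a separate gate for each dose, and Protocol 6.2 asks which groups are efficient. On that reading any dose short of 4 is dropped, and alpha 0.139 with power 0.801 is what was promised. This stands as a reasonable guess at the intent. But the sentence rejects *the drug*, not the dose, and neither document attaches the figures to a single dose.

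The second reply is that non-adjustment is declared openly and explained by the proof-of-concept setting. That also stands. At alpha 0.15 without adjustment, a drug-level rate near 0.23 is the natural consequence of an open choice, and nothing here requires a multiplicity correction. The declaration does not, however, state the resulting rate or settle what *any* means.

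A reader might combine the two results and say that the design has both a 23% false-go rate and 13% power. No reading gives both. If one dose suffices, only alpha is exceeded; if both are required, only power falls short, and the false-go rate of 0.047 is well inside 0.15.

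A reader might also say that per-dose alpha holds only near a 20% placebo rate. It holds at lower rates too (0.073 at 10%) and fails only above about 22%.

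**Conclusion.** The final rule is wrong as written. Taken literally it gives power of 0.13 with one working dose and about 0.68 with two, against a stated 80%, and it contradicts both the stage I gate and the aim of identifying effective dose groups. If one successful dose carries the drug forward, power is adequate (0.81 to 0.92), but the drug-level false-go rate is 0.23 at a common 20% response. It ranges from 0.13 at 10% to 0.30 at 50%. The stated pair is met only dose by dose, with a placebo rate up to about 22%.

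These figures assume full arms of 23 and 10, independent subjects, and true rates of 20% for an inactive arm and 40% for an active one unless stated otherwise. The documents give no placebo rate, so 0.23 should be quoted with its range.

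It would go too far to infer that the sample size calculation is mistaken or that the trial reached a wrong decision. The single-dose calculation reproduces. SAP 5.4 says the interim results did not meet the protocol requirement and the study was terminated, so the cut of 4 on accumulated responders appears never to have been applied. What remains concerns the planned design and any report that cites its alpha and power. It should be corrected, but it is not among the most serious kind of finding.

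**What to change.** Reword Protocol 8.1 and SAP 5.3.4 along these lines: *A dose is promising if its cumulative difference in responders from placebo is at least 4; the drug is rejected only if neither dose reaches 4.*

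Add that 0.15 and 80% are per-dose figures at a placebo response of about 20%. Report the unadjusted drug-level false-go rate beside them: 0.23 at 20%, 0.13 at 10%, and 0.28 to 0.30 at 30% to 50%. The sample size and the cut of 4 can stay.

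The cost is a less favourable published false-go figure and an amendment in two sections, with the regulatory and IRB submission that Protocol 10.2 requires for a non-administrative change. If the documents are no longer open to amendment, the same statement belongs in the study report wherever alpha 0.15 and 80% power are cited. No extra subjects are needed.

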5.3 Statistical Methods Planned in the Protocol and Determination of Sample Size

5.3.1 Populations for Analysis

The INTENT-TO-TREAT (ITT) POPULATION consists of all randomized subjects who receive at least one dose of study medication and fulfill all inclusion, exclusion criteria and have any post-baseline safety data collected.

The PER-PROTOCOL (PP) POPULATION is defined as (1) The drug compliance is at least 80% (2) Subjects have completed data to determine the primary endpoint. (3) Subjects cannot have protocol deviation. The protocol deviation will be defined as (1) Inclusion or exclusion criteria not satisfied. (2) Not permitted concomitant medications (3) Wrong randomized treatment prescribed.

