6.2 Data Sets Analyzed

Two study populations are intention-to-treat (ITT) population and per-protocol (PP) populations which are defined in section 5.3.1.

The efficacy evaluations will be performed on both of the ITT and PP datasets while the safety evaluations will be performed on the ITT dataset. The primary conclusion will be made for the primary endpoint on the ITT population. Demographic and baseline (Visit 2) characteristics will be performed on the ITT population.

Sample size, mean, 95% confidence interval of mean, median, standard deviation, inter-quartile range, maximum and minimum will be summarized for continuous variables. For categorical variables, the frequency and percentage will be provided.

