6.6 Analysis of Efficacy

6.6.1 Primary Efficacy Endpoint

An improvement of 40% or greater response rate from baseline in treatment group is considered effective and worth further study. The endpoint will be analyzed by checking if the difference of counts of responder is larger than 0 between PDC-1421 arm and placebo arm. Missing data caused by premature termination will be utilized the last observation carried forward (LOCF).

The response rate in the ADHD-RS-IV total score is defined as the following formula.

$$\text{Response rate} = \frac{\text{score}_{\text{visit}} - \text{score}_{\text{baseline}}}{\text{score}_{\text{baseline}}}$$

and the responder is defined as

$$\text{Responder : response rate} \geq 40\%$$

The descriptive statistics will include the proportion of subjects who achieved at least 40% improvement of the ADHD-RS-IV total score at Visit 6 by treatment group and placebo group. The frequency distribution of pre-treatment and post-treatment will also be tabulate and report in bar graph.

The primary measure of efficacy was the ADHD-RS-IV, consisting of 18 items designed to reflect current symptomatology of ADHD based on DSM-IV-TR criteria. Each item is scored on a 4-point scale ranging from 0 (reflecting no symptoms) to 3 (reflecting sever symptoms) with total scores ranging from 0 to 54, which is calculated by summing up scores of subscales. The 18 items may be grouped into 2 subscales:

- For inattention (IA) subscale raw score: Add the odd-numbered 9 items. Higher score indicate severe inattention symptoms.
- For hyperactivity-impulsivity (HI) subscale raw score: Add the even-numbered 9 items. Higher score indicate severe hyperactivity-impulsivity symptoms.
- To obtain the total raw score: Add the IA and HI subscale raw scores.

Following SAS procedures will be applied for chi-Square test between arms.

```
%macro;  
proc freq data = ____;  
    table response*treatment/chisq;  
    output out = chiqtest chisq;  
run;  
%mend;
```

When there has a missing value issue, the following LOCF SAS procedures will be applied.

```
%macro;  
DTAT locf1;  
    LENGTH dtype $15;  
    RETAIN retain;  
    SET lab;  
    BY usubjid visit;  
  
    IF FIRST . visit ^=0 THEN retain = . ;  
    IF qsstresc NE . THEN retain = qsstresc;  
    IF qsstresc= . THEN DO;  
        qsstresclocf = retain;  
        dtype = 'LOCF';  
    END;  
    ELSE qsstresclocf = qsstresc;  
RUN;  
%mend;
```

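### Both go rules compare raw responder counts, so if the analysed arms differ by even one subject, either alpha 0.15 or power 80% is missed, and the plan has no rule for unequal arms

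*Protocol*

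**What the plan says.** Protocol 8.1 adopts a randomised two-stage design with alpha 0.15 and power 80%. The drug counts as non-effective if the response rate "is 20 % or lower and is worth further study if the response rate is 40 % or higher".

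- Stage I: "At the first stage, we recruit 23 subjects for each group". A dose goes forward "If the difference between the numbers of responders for any PDC-1421 arm and control arm is greater or equal to 0".
- Final: 10 more per arm, then "If the difference between the accumulated numbers of responders for any PDC-1421 arm and control arm is less than 4, we reject the drug".

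SAP 5.3.4 repeats these cut-offs. SAP 6.6.1 describes the primary analysis as "checking if the difference of counts of responder is larger than 0". No denominator appears in any of these places.

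Protocol 8.1 does not name the analysis set for the rule. SAP 6.2 does so for the conclusion: "The primary conclusion will be made for the primary endpoint on the ITT population". Under Protocol 8.3 the ITT set leaves out randomised subjects with no dose or no post-baseline safety data. SAP 5.3.1 further requires that subjects "fulfill all inclusion, exclusion criteria and have any post-baseline safety data collected". Protocol 3.1 targets 99 ITT subjects in total but gives no number per arm. LOCF is planned for missing data (Protocol 8.3 and 8.4, SAP 6.8.1). SAP 5.4 reports that the interim result did not meet the protocol's requirement and that the study was terminated.

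**The concern.** A difference in counts measures the treatment effect only if both arms have the same number of subjects. At a common response rate p, the expected difference is p × (drug n − placebo n), which is zero only for equal arms. A smaller placebo arm therefore favours the drug, and a smaller drug arm works against it. At 33 v 29 and a 20% common rate the offset is 0.2 × 4 = 0.8 responders, one fifth of the cut-off of 4.

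The cut-offs are fixed for 23 and 33 per arm, while the ITT definition allows the analysed arms to differ. The go/no-go decision would then depend partly on which arm lost subjects.

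**Working it through.** **Inputs.** Arm sizes 23, then 33 cumulative; cut-offs 0 and 4; rates 20% and 40%; alpha 0.15; power 80% (all Protocol 8.1). The placebo rate is not given separately; I assume 20%. The rule is one-sided by construction. No loss rate is stated, so every unequal arm size below is an assumption. All figures are for one dose against placebo.

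**Formula.** Let D1 and D2 be the drug-minus-placebo responder differences in stages I and II, each a difference of two independent binomial counts. Then P(go) = Σ P(D1 = i) × P(D2 = j) over i ≥ 0 and i + j ≥ 4. Alpha is P(go) at 20% v 20%; power is P(go) at 40% v 20%.

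**Step 1: the plan's own figure.** At 23 + 10 per arm, alpha = 0.1388 and power = 0.8009. Both limits are met. The slack is 0.0112 on alpha and 0.0009 on power.

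**Step 2: the same count rule with unequal arms (drug v placebo).**

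| Stage I | Cumulative | Alpha | Power |
|---|---|---|---|
| 23 v 23 | 33 v 33 | 0.139 | 0.801 |
| 23 v 22 | 33 v 32 | 0.151 | 0.818 |
| 22 v 23 | 32 v 33 | 0.124 | 0.771 |
| 23 v 20 | 33 v 29 | 0.193 | 0.863 |
| 20 v 23 | 29 v 33 | 0.084 | 0.665 |

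Intermediate cases lie between these: 33 v 30 gives alpha 0.178, and 30 v 33 gives power 0.704. Losing the single subject in stage II instead of stage I changes little (alpha 0.151; power 0.773). Equal losses also cost power (32 v 32: alpha 0.135, power 0.789), but that is lost sample size, not a tilt towards one arm.

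**Step 3: the stage I rule, P(D1 ≥ 0).**

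| Drug v placebo | 20% v 20% | 40% v 20% |
|---|---|---|
| 23 v 23 | 0.574 | 0.953 |
| 23 v 20 | 0.663 | 0.973 |
| 20 v 23 | 0.486 | 0.909 |

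**Step 4: possible remedies.** In each case stage I requires a proportion difference of at least 0.

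*Fixed final cut-off of 4/33 = 0.121.* At 33 v 32 this gives alpha 0.090 and power 0.734. With unequal arms the attainable differences in proportion change, so a fixed cut-off can be much too strict.

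*Final cut-off recomputed* as the smallest attainable difference with alpha at most 0.15 at a 20% common rate:

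| Cumulative | Cut-off (about) | Alpha | Power |
|---|---|---|---|
| 33 v 32 | 0.090 | 0.148 | 0.809 |
| 32 v 33 | 0.099 | 0.149 | 0.833 |
| 33 v 29 | 0.105 | 0.140 | 0.787 |
| 29 v 33 | 0.100 | 0.148 | 0.797 |

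Other splits can do somewhat worse: 33 v 31 (23 v 22, then 10 v 9) gives alpha 0.145 and power 0.764.

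**The case against.** The strongest reply is that the design is sound as planned. Allocation is 1:1:1, the ITT exclusions are narrow, LOCF keeps later dropouts in the set, and 99 ITT subjects are targeted. Unequal arms are possible but not certain, and a loss of 4 of 33 from one arm only is my choice of scenario. All of that stands.

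A second reply is that the alpha breach is conditional on the realised arm sizes. If each subject has the same 5% chance of exclusion in every arm, the rates of counted responders become 0.19 v 0.19 or 0.38 v 0.19, and the rule averages alpha 0.134 and power 0.778. This also stands: on average, exclusions unrelated to arm cost power, not alpha. Alpha rises when the realised placebo arm is smaller, or systematically when exclusions are commoner on placebo. The reported decision is nonetheless made at one realised pair of arm sizes.

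The documents do not support four stronger readings:

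- *The stated alpha and power are simply wrong.* They are met at 33 v 33.
- *Both limits fail together.* In every one-arm loss computed, only one does: fewer placebo subjects raise alpha and power, and fewer drug subjects lower both.
- *Alpha reaches 0.308.* That is 33 v 29 at a 40% common rate, outside the plan's 20% null. Equal arms already give 0.187 there, which is a separate question.
- *The interim decision was wrong.* Neither document gives the interim counts or arm sizes.

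**Conclusion.** The point holds as a conditional weakness. Both rules use raw counts calibrated to 23 and 33 per arm, the ITT set can leave unequal arms, and no adjustment is planned. A difference of one subject misses a limit narrowly for alpha (0.151) and more clearly for power (0.771). At an assumed difference of four, alpha is 0.193 or power 0.665, depending on which arm is smaller.

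Because the trial ended at the interim, the cut-off of 4 was not reached and the practical weight falls on stage I. At 20% v 20%, the chance that one dose passes moves from 0.574 to 0.663 or 0.486 with three subjects missing from one arm. At 40% v 20%, the chance that an effective dose fails rises from 4.7% to 9.1% at 20 v 23.

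These figures assume a 20% placebo rate, independent binomial responses, one dose at a time, and the Protocol 8.1 reading of stage I (at least 0).

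**What to change.** In Protocol 8.1 and SAP 5.3.4 and 6.6.1:

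1. Name the analysis set to which the rule applies.
2. State both rules as differences in response proportion, with at least 0 at stage I. Align SAP 6.6.1, which requires more than 0, with Protocol 8.1 and SAP 5.3.4.
3. If the arms differ, recompute the final cut-off exactly at the realised sizes so that alpha is at most 0.15 at a 20% common rate.

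The cost is wording, one short exact calculation, and some power: 0.787 to 0.833 in the four main cases, and 0.764 at 33 v 31. The stage I proportion rule largely removes the dependence on which arm is smaller (pass probability at 20% v 20%: 0.511 at 23 v 20 and 0.489 at 20 v 23). It is stricter than 0.574 because ties become rarer; at 40% v 20% the chance of passing is 0.931 and 0.921, against 0.953 with equal arms.

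Counting excluded subjects as non-responders is not a substitute. A subject without data adds no responder either way, so the count difference is unchanged, and extending the rule to dropouts would override the planned LOCF.

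For this trial the rule can no longer be changed. The report should give the interim responder counts by arm with their denominators, and the difference in proportions for each dose.
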